- VI. Any acute or chronic condition or other disease that, in the opinion of the Investigator, would limit the subject's ability to complete and/or participate in this clinical study.
- VII. Significant untreated psychiatric dysfunction based upon screening. Hospital Anxiety and Depression Inventory (HAD) score >11 on depression scale, a self-administered alcoholism screening test (AUDIT-C) score >4 in men or >3 in women, and difficulties with substance or eating disorders determined by the Questionnaire on Eating and Weight Patterns (binge eating disorders and bulimia); will mean the participant will be excluded and given a referral letter to his/her primary care doctor for further appraisal and follow-up. The provider will review the patient's alcohol intake over the past few months to confirm accuracy and determine study eligibility.

VII. Principal Investigator discretion.

[figure not shown]
Intervention:

CBAS 500 mg tablets will be supplied by Bilarm Health Inc.. Subjects will take medication or placebo orally twice daily on an empty stomach, 30 minutes prior to breakfast and evening dinner for 90 +/- 5 days. Patients on the medication will receive 500 mg twice daily during their first week and 1000 mg twice daily for the rest of the study.

Methods:

Participants will keep food, appetite, and activity diaries for one week prior to baseline test day[11]. On randomization day they will also receive the randomized medication (delayed release IC-CBAS or placebo). A full medical history and physical exam will be performed and recorded, and a low-calorie diet will be suggested during this visit.

On Day 90 (+/- 5 days), subjects will repeat obesity phenotyping protocol at the exit visit [11] as described previously but will receive the study medication/placebo 30 minutes prior to the test meal.

*Visit 1, 3, 4 and 6 can be conducted at the Clinical Research and Trials Unit (CRTU)in the [REDACTED] at Mayo Clinic in Rochester, MN.

Visit 2 and 5 can be conducted at the CRTU or on [REDACTED]

Screening and Consent (virtual):

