Height, weight, blood pressure, heart and respiratory rates, waist and hip ratio, waist circumference, and temperature.
- Baseline and follow-up characteristics studies:
- Methods of metabolic studies:
 - o Body composition will be measured by DEXA (dual energy x-ray absorptiometry).
 - o Resting energy expenditure was assessed by indirect calorimetry with a ventilated hood (Parvo Medics, Sandy, UT).

- Gastric emptying (GE) of solids by scintigraphy [9] [8, 11] Images will be acquired at 0, 30, 60, 90, 120 and 240 minutes following the normal clinical gastric emptying testing protocol without a push meal.
- Satiation will be measured by *ad-libitum* meal to measure total caloric intake and macronutrient distribution in the chosen food. Satiation will be reported in calories consumed at fullness (satiation) [8] [11].
- Appetite sensations by visual analog score fasting and every 30 minutes after the standard meal for GE and the Satiation test up to 2 hours [8, 11].
- Blood samples: The fasting blood samples will be collected during the gastric emptying meal and stored at -70° C freezer. We will analyze plasma glucose, insulin, C-peptide, GLP-1, PYY₃₋₃₆, OXM, FGF-19, 7- α -C4, Adiponectin, Leptin, CCK, Pancreatic Polypeptide (PP), serum bile acids, short chain fatty acids, amino acids[2, 8]. Samples collection, handling, and storage: Samples will be collected after an overnight fast (of at least 8 hours) in the morning. Plasma will be preserved following standard guidelines and protein degradation inhibitors, kallikrein and DPP-IV inhibitors will be added to preserve the samples. Samples will be stored at -80°C in the PI's laboratory. Plasma hormones and proteomics by radioimmunoassay and/or mass spectrometry measured fasting, postprandial, and every 30 minutes for 6 hours. The primary endpoint being the peak postprandial level (test should be done simultaneously to GE).
- Blood DNA for genome wide association studies (GWAS). These samples will be stored for future research.
- Stool samples: One random stool will be collected at baseline and after treatment for fecal bile acids, short chains fatty acids and microbiome.
- Participants with childbearing potential will undergo a pregnancy test.
- Self-administered questionnaires assessing affect, physical activity levels, attitudes, body image, diet, and eating behavior; details of each questionnaire are provided below.

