All participants will meet with a study physician as standard of care in clinical practice. All participants will guided to 1) Diet: Reduce dietary intake below that required for energy balance by consuming 1200 calories per day for women and 1400 calories per day for men; 2) Physical Activity: reach the goal of 10,000 steps or more per day; 3) Exercise: reach the goal of 150 minutes or more of cardiovascular exercise/week; 4) Limit consumption of liquid calories (i.e. sodas, juices, alcohol, etc.).

- **Visit 2: Colonoscopy #1 and Randomization**

- Visit 2 will only be completed in the first 6 patients of each group who are willing to consent to both colonoscopy visits.
- Visit 2 will occur 3- 5 days of Visit 1. Participants will receive a bowel prep (Movi-prep) during Visit 1 and follow standard colonoscopy preparation guides. The next day, after an overnight fasting, a colonoscopy with terminal ileum intubation will be performed. The colonoscopy will be done in the GI clinical or research unit and will be supported by sedation based on patients' characteristics (i.e., conscious sedation vs. anesthesia supported sedation). During the procedure, 8 biopsies will be obtained from the ilium, right and left colon.
- Randomization and treatment:
Randomization will be performed by the research pharmacy upon notification by the study coordinator. Treatments will be allocated at a 1:1 ratio stratified within low, medium, or high gastric emptying (T1/2) rates, based on sex-specific thresholds. The stratification group will be determined by the study coordinator and communicated to the pharmacist. A computer application will provide the randomized assignment based on a randomization schedule created by the study statistician. Only the study statistician will have access to the complete schedule. Other study personnel and the subject will be blinded to assigned treatment.

Patients will receive study medication (active or placebo), and they will be given verbal instructions on how they should take their medications. Subjects will take medication or placebo orally twice daily on an empty stomach, 30 minutes prior to breakfast and evening dinner for 90 (+/- 5) days. Patients will be instructed to start the medication after visit 2 (colonoscopy).

- **Visit 3: Study Team visit**

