- Participants will meet with the study team (either in person at the CRTU or virtually) approximately 30 days after visit 2. The study team will assess adverse events, medication compliance, and perform a new medication dispensation (if visit is virtual the medication will be shipped to the participant's preferred address).

- **Visit 4: Study Team visit**

Participants will meet with the study team (either in person at the CRTU or virtually) approximately 30 days after visit 3. The study team will assess adverse events, medication compliance, and perform a new medication dispensation (if visit is virtual the medication will be shipped to the participant's preferred address).

- **Visit 5: Colonoscopy #2**

- Visit 5 will only be completed in the first 6 patients of each group who are willing to consent to both colonoscopy visits.
 - Participants will receive a bowel prep (Movi-prep) during visit 5 and follow standard colonoscopy preparation guides. The next day, after an overnight fasting, a colonoscopy with terminal ileum intubation will be performed. The colonoscopy will be done in the GI clinical or research unit and will be supported by sedation based on patients' characteristics (i.e., conscious sedation vs. anesthesia supported sedation). During the procedure, 8 biopsies will be obtained from the ilium, right and left colon.

- **Visit 6 – Exit Phenotyping**

- Visit 6 will occur within 7 days of Visit 3. Phenotyping will be performed as at the baseline phenotyping visit including the questionnaires performed in screening visit.

Primary Endpoint:

The primary endpoint is EEC function measured through satiety hormones' (GLP-1 & PYY AUC and absolute plasma value curves) comparison between intervention and placebo groups at day 90 in APS-OB phenotype participants.

Secondary Endpoint:

Evaluation of obesity phenotypes through gastric emptying T_{1/2} for solids, satiety sensation with a visual analogue scale (VAS), fullness (VAS), hunger (VAS), desire to eat (VAS), appetite overall score (VAS), ad-libitum buffet meal food intake (kcal), microbial changes, behavioral questionnaires, energy expenditure, and body weight in APS-OB phenotype participants intervened with IC-CBAS, compared to placebo.

Statistical Analysis:

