The primary analysis will compare AUC values between treatment and placebo groups after 90 days of IC-CBAS. Based on the previous study by Calderon et al.[1], we calculated a sample size of 36 subjects. They reported GLP-1 AUC significant difference between intervention and placebo group of 3223 mg/dl. We aim to detect a mean difference in AUC of 3223mg/dl and utilized their IQR to calculate a standard deviation of 3125mg/dl. To have 80% power to detect a difference of 3223mg/dl with a two-sample t-test would require 12 subjects per group. In order to allow for up to 30% dropout, we will enroll 36 subjects total. The effect on weight loss will be evaluated using analysis of covariance (ANCOVA) models, with relative weight loss as the dependent variable, adjusting for gastric emptying (T_{1/2}, min) and gender. Any power lost on degrees of freedom spent on covariate parameter estimation should be more than reclaimed by reduced error variation. For the rest of the endpoints we will compare the data on gastric emptying, satiation parameters, appetite scores, body composition, energy expenditure, GI hormones, bile acids and microbiota between intervention vs. placebo, using the same ANCOVA model. Transformations will be employed as needed for heavily skewed distributions. All treatment effect estimates will be reported with 95% confidence intervals.

POTENTIAL PITFALLS AND PRECAUTIONS TAKEN:

Potential pitfalls of minor significance in this study are:

- **Selection bias** - Participants willing to participate will likely be more motivated to lose weight than the general population. Randomization, double blind will avoid any selection bias;
- **Potential for type II error** - The sample sizes have been based on appropriate statistical power with allowance for drop out. Estimates of variation have been thoroughly characterized in the prior literature from our lab; and other internal and external studies for weight loss at 12 weeks.
- **Feasibility** - We have identified a cohort of people in our community who have obesity, abnormal satiety phenotype, and are willing to participate. We have the experience to successfully recruit 36 participants for the study.

Human Studies Aspects

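### Baseline GLP-1 and PYY AUC can be derived from Visit 1 but enters no analysis, and the primary AUC model is not clearly named, so available precision may be lost

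*Combined protocol and SAP*

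**What the plan says.** **Data collected.** Under Visit 1 (Baseline phenotype), plasma hormones, including GLP-1 and PYY, are "measured fasting, postprandial, and every 30 minutes for 6 hours". The Visit 6 section states: "Phenotyping will be performed as at the baseline phenotyping visit". Visit 1 precedes treatment; the Visit 2 section states: "Patients will be instructed to start the medication after visit 2 (colonoscopy". A 6-hour AUC of the same kind is therefore available before treatment and at exit.

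**Analysis.** The Primary Endpoint section compares GLP-1 and PYY between arms at day 90. The Statistical Analysis section adds: "The primary analysis will compare AUC values between treatment and placebo groups after 90 days of IC-CBAS". It then sizes the trial with a two-sample t-test on GLP-1 AUC and introduces an ANCOVA for relative weight loss, adjusting for T1/2 and gender. That model is extended: "For the rest of the endpoints we will compare the data on gastric emptying", followed by a list that ends "GI hormones, bile acids and microbiota between intervention vs. placebo, using the same ANCOVA model". In support of covariates it argues: "Any power lost on degrees of freedom spent on covariate parameter estimation should be more than reclaimed by reduced error variation".

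No section defines a change from baseline in AUC or names baseline AUC as a covariate.

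**The concern.** There are two linked gaps.

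- **The model for the primary AUC is not settled.** The extension sentence concerns endpoints other than the primary, which points to the t-test, yet its list includes GI hormones, which points to ANCOVA on T1/2 and gender. The two can give different p-values on the same data, and the choice stays open until data are seen.
- **Neither reading uses the outcome's own pre-treatment value.** That value is already collected and is an obvious candidate to explain outcome variance. The plan's own argument for covariates applies to it at least as naturally as to T1/2 and gender. The other endpoints in the list also lack their own baseline. Gastric emptying is an exception if the T1/2 covariate is the baseline value. Relative weight loss already uses baseline weight in its definition.

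At stake is power in a trial that may finish with 12 per group.

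**Working it through.** **Inputs.** From Statistical Analysis: difference 3223, SD 3125, 12 completers per group, 36 enrolled (18 per group) to allow 30% dropout. That section gives no alpha for the AUC calculation; two-sided 0.05 is assumed, in line with its 95% confidence intervals. No inputs are given for PYY, so all figures are for GLP-1. The correlation ρ between baseline and exit AUC is not in the documents; 0 to 0.7 is tried.

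**Step 1: the plan's own figure.** d = 3223/3125 = 1.031. The normal approximation gives n = 2 × [3125 × (1.960 + 0.842)/3223]² = 14.8, so 15 per group; the exact t-test needs 16. The stated 12 is met only with a one-sided 0.05 normal approximation (the one-sided t-test needs 13), and the plan states no one-sided test. The dropout step reproduces: 12/0.7 = 17.1, so 18 per group. Exact two-sided t-test power, with noncentrality d√(n/2):

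- 12 per group: 1.031 × √6 = 2.53 on 22 df, power 67.5%
- 18 per group: 1.031 × √9 = 3.09 on 34 df, power 85.2%

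**Step 2: closed-form effect of baseline AUC.** Residual SD = 3125 × √(1 − ρ²), which is 2981, 2706 and 2232 at ρ = 0.3, 0.5 and 0.7. With one df lost (21 df), power at 12 per group is 71.4%, 79.4% and 92.1%. This ignores chance imbalance in the covariate, which costs something in a trial this small, so simulation is the better guide.

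**Step 3: simulation.** 40,000 trials per cell, normal data, T1/2 and sex unpredictive, Monte Carlo SE about 0.2 points. Chance means T1/2 and sex are balanced only by chance; balanced means T1/2 tertile and sex are balanced between arms. Power in %:

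| ρ | Baseline AUC only, n=12 | Three covariates, n=12, chance | Three covariates, n=12, balanced | Three covariates, n=18, chance | Three covariates, n=18, balanced |
|---|---|---|---|---|---|
| 0 | 65.3 | 60.3 | 64.3 | 81.8 | 83.9 |
| 0.2 | 67.0 | 63.1 | 66.3 | 83.2 | 85.0 |
| 0.3 | 69.4 | 65.0 | 68.0 | 85.1 | 86.6 |
| 0.4 | 72.9 | 67.8 | 71.4 | 87.7 | 89.6 |
| 0.5 | 76.8 | 73.0 | 76.7 | 91.0 | 92.5 |
| 0.6 | 83.2 | 79.6 | 82.6 | 94.5 | 95.6 |
| 0.7 | 90.6 | 87.4 | 90.0 | 97.9 | 98.3 |

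**Step 4: comparators at 12 per group.**

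- Against the t-test (67.5%), the three-covariate model breaks even at ρ of about 0.3 (balanced) to 0.4 (chance).
- Against the plan's ANCOVA on T1/2 and gender alone (63.1% chance, 66.6% balanced), adding baseline AUC breaks even at about 0.2.

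**Step 5: interval width.** The mean 95% CI half-width at 12 per group is 2618 unadjusted. With three covariates it is 2460 (chance) or 2356 (balanced) at ρ = 0.5, that is 2460/2618 = 0.94 and 2356/2618 = 0.90, or 6–10% narrower. At ρ = 0.7 it is 2032 or 1940.

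**The case against.** The strongest reply is that this is a preference for efficiency. A day-90 comparison of randomized arms is valid and matches the stated endpoint. That stands, and it limits the severity.

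The gain also depends on a correlation nobody has given, and there are reasons it could be low. At exit, participants "will receive the study medication/placebo 30 minutes prior to the test meal", whereas baseline is untreated. Both arms follow a diet and exercise programme for the duration, and enrolment is restricted to a phenotype described by low GLP-1 and PYY, which may narrow the baseline range. At ρ = 0 the proposed model loses power. This stands as a caution; it is why break-even points are shown.

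The plan does not say whether SD 3125 describes an end-of-treatment AUC, a change or an incremental AUC. If it is not the SD of the raw day-90 AUC, the sizes above are misstated. That is a fair limit on the figures, although the plan itself uses this SD in its t-test.

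In the simulation, baseline AUC alone matches or beats the three-covariate model because T1/2 and sex were made unpredictive. The case for keeping them is that randomization is stratified on sex-specific T1/2 levels and that the plan already adjusts for both.

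The t-test is arguably the natural reading, with GI hormones meaning the non-primary ones. That is tenable, but the text does not exclude the other reading. Finally, using baseline weight as a divisor is not covariate adjustment; it only means that baseline weight is not ignored for that endpoint.

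**Conclusion.** The concern holds. A pre-treatment GLP-1 and PYY AUC can be derived, no specified analysis uses it, and the primary AUC model can be read two ways. Validity is not threatened. At 12 completers per group, adding baseline AUC to T1/2 and sex changes GLP-1 power from the t-test's 67.5% to 73–77% if ρ is 0.5 and to 87–90% if it is 0.7. At 0.3 there is essentially no gain (65–68%), and at 0 there is a loss (60–64%). At 18 per group the t-test has 85%, and the adjusted model has 91–93% at ρ = 0.5.

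These sizes assume two-sided 0.05, normal data, SD 3125 as the SD of day-90 AUC, and unpredictive T1/2 and sex. Every correlation is an assumption. The need to name the primary model depends on none of these. The change should be made, but it is not critical; confidence in the size of the benefit is medium.

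**What to change.** Before unblinding, state one primary model form for the hormone AUC: ANCOVA of day-90 AUC on treatment and baseline AUC, with T1/2 and sex as in the existing ANCOVA. If a log scale is used for skewness, apply it to both baseline and day-90 values. Say explicitly that this model, not the sentence on the remaining endpoints, governs the primary AUC. For each other endpoint measured at both visits, add its own baseline value as a covariate; relative weight loss can stay as it is.

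The cost is SAP wording only, with no new data. If no covariate proves predictive, the power loss against a t-test at 12 per group is about 2 points for baseline AUC alone (67.5 − 65.3). For all three covariates it is about 3 points (67.5 − 64.3, balanced) to 7 points (67.5 − 60.3, chance balance). At 18 per group it is about 1 to 3 points (85.2 − 83.9 and 85.2 − 81.8). If the sponsor has baseline-to-exit correlations from its previous trial, they should be cited to support the choice.

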This is a single-center, placebo-controlled, double-blinded, parallel-group, randomized 90 days (+/- 5 days) trial to study the effect of IC-CBAS 500 mg and 1000 mg BID on EEC function, satiety perception, body weight and satiety GI hormones, in patients with APS-OB phenotype. A lifestyle intervention will be provided. These consist of an obesity physician consult, a low-calorie diet instructed by a member of the study team, and physical activity and behavioral suggestions. These interventions should last at least the length of the study. In addition, this study will include 2 colonoscopies at the beginning (i.e., before medication/placebo start) and at the end of the study (i.e., after last dose of medication/placebo) in the first 6 patients in each group willing to consent to the colonoscopies (12 patients; 24 colonoscopies in total). Participants will receive a bowel prep (Movi-prep) and follow standard colonoscopy preparation guides. The next day, after an overnight fasting, a colonoscopy with terminal ileum intubation will be performed. The colonoscopy will be done in the GI clinical or research unit and will be supported by sedation based on patients' characteristics (i.e., conscious sedation vs. anesthesia supported sedation). During the procedure, 8 biopsies will be obtained from the ilium, right and left colon. We will include otherwise healthy patients with a BMI > 30 kg/m², age range 18-65 years, and APS-OB phenotype. Based on the results of our previous trial comparing weight loss in exenatide therapy vs placebo [2], we calculated a sample size of 18 participants per group (total of 36) with 80% power, 0.05 alpha to detect a 1 kg difference between treatment and placebo groups.

Study Intervention:

Ileocolonic-release conjugated bile acid 500mg tablets will be provided by Bilarm Health Inc., San Diego, CA.

Anticipated Results:

In comparison with placebo, IC-CBAS will result in improved EEC function, increased postprandial incretin secretion, and weight loss when compared to placebo.

Significance:

We expect to demonstrate that delayed IC-CBAS increases satiety, restoring satiety in patients with APS-OB phenotype. This study will provide the basis for future pharmacological studies, exploring the effect of luminal enteroendocrine secretagogues in patients with obesity and APS-OB phenotype.

BACKGROUND:

Overview:

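### The primary AUC sample size states no alpha or sidedness; at two-sided 5% its own inputs need 16 evaluable per group, and the stated 12 gives 67.5% power, not 80%

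*Combined protocol and SAP*

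**What the plan says.** In the Statistical Analysis section, the inputs for the primary comparison are given as: "We aim to detect a mean difference in AUC of 3223mg/dl and utilized their IQR to calculate a standard deviation of 3125mg/dl". The resulting size is: "To have 80% power to detect a difference of 3223mg/dl with a two-sample t-test would require 12 subjects per group". It is then raised for attrition: "In order to allow for up to 30% dropout, we will enroll 36 subjects total". No alpha and no sidedness accompany this calculation.

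The same section ends with a reporting rule for every comparison: "All treatment effect estimates will be reported with 95% confidence intervals".

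The only alpha in the document is in the Study design paragraph of the synopsis. It belongs to a different calculation, on body weight, also reaching 18 per group: "with 80% power, 0.05 alpha to detect a 1 kg difference between treatment and placebo groups". That passage gives no sidedness either.

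The section on potential pitfalls lists type II error among the pitfalls of minor significance, on this ground: "The sample sizes have been based on appropriate statistical power with allowance for drop out".

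**The concern.** A two-sample sample size depends on the standardised difference, the power, the significance level and the sidedness. The plan gives the first two and omits the others, so the 12 cannot be reproduced from what is declared. The customary completion, two-sided 5%, does not lead to 12.

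This is the only sizing given for the primary endpoint, and the enrolment target of 36 is derived from it. If the 12 is too small, the dropout allowance does not protect 80% power. A null primary result would then be read as coming from a trial with a 20% chance of missing the planned effect, when the real chance at the planned dropout is nearer 30%. The protocol intends this trial to inform larger ones, so that misreading would carry forward.

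**Working it through.** **Inputs (Statistical Analysis section).** Difference 3223; SD 3125; power 80%; two-sample t-test; 36 enrolled, dropout up to 30%. Allocation is 1:1 (randomisation text under Visit 2), so 18 per group. Standardised difference d = 3223/3125 = 1.0314, so d² = 1.0637.

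**Step 1. Reproducing the plan's 12.** Normal approximation: n per group = 2(z_α + z_β)²/d², with z_β = 0.8416.
- One-sided 5% (z = 1.6449): 2 × (2.4865)²/1.0637 = 11.62, rounded up to 12.
- Two-sided 5% (z = 1.9600): 2 × (2.8016)²/1.0637 = 14.76, rounded up to 15.

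So 12 comes from a one-sided 5% normal approximation (equivalently, two-sided 10%). The dropout step then follows: 12/0.70 = 17.1, rounded up to 18 per group, 36 in total.

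**Step 2. The test actually named.** Power comes from the noncentral t distribution with n₁ + n₂ − 2 degrees of freedom and noncentrality d√[n₁n₂/(n₁ + n₂)]. At 12/12 the noncentrality is 1.0314 × √6 = 2.526 on 22 degrees of freedom. The critical value is 2.074 two-sided and 1.717 one-sided.

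| Evaluable per group | Two-sided 5% | One-sided 5% |
|---|---|---|
| 12/12 | 67.5% | 78.9% |
| 13/12 | 69.4% | 80.4% |
| 13/13 | 71.3% | 81.8% |
| 15/15 | 77.8% | 86.7% |
| 16/16 | 80.6% | 88.6% |
| 18/18 | 85.2% | 91.7% |

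The exact solutions for 80% power are 15.78 (so 16 per group) two-sided and 12.36 (so 13 per group) one-sided. Simulation with 200,000 trials per setting agreed for the two-sided figures checked: 67.4% at 12/12, 69.5% at 13/12, 71.4% at 13/13, 80.6% at 16/16 and 85.2% at 18/18.

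**Step 3. What 36 enrolled delivers at two-sided 5%.**
- No dropout (18/18): 85.2%.
- 16 of 18 per group complete (2/18 = 11% dropout): 80.6%.
- 30% dropout: 36 × 0.70 = 25.2 completers, giving 69.4% (13/12) to 71.3% (13/13).
- 12 per group complete (12/36 = 33% dropout): 67.5%.

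**Step 4. What would make 12 correct at two-sided 5%.** At 12/12 the standardised difference detectable with 80% power is 1.1968. That is a difference of 1.1968 × 3125 = 3740 rather than 3223, or an SD of 3223/1.1968 = 2693, which is 14% below the stated 3125.

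**Step 5. Holding 80% at 30% dropout.** 16/0.70 = 22.9, so 23 per group, 46 in total.

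**The case against.** The strongest reply is that this is an omission and not an arithmetic error. The hypotheses are directional, no passage declares a two-sided test, and 12 does follow from a one-sided 5% calculation. The 95% intervals are a general reporting rule and only indirect evidence of the intended test. This stands in part: the figure of 16 is conditional on two-sided 5%. It does not save the 12. The plan names a t-test, and the one-sided solution of 12.36 reaches 12 only by rounding down, leaving 78.9%. A one-sided 5% test also corresponds to a 90% two-sided interval, not the 95% interval promised. On the one-sided reading, however, the enrolment of 36 does hold 80% at 30% dropout (80.4% at 13/12).

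A second reply concerns the dropout figures. Read strictly, up to 30% of 36 means at most 10 losses, so 26 complete and power is about 71%; 67.5% requires 33% dropout. This is fair as a refinement. The 67.5% tests the stated 12 per group, and the trial's power at its planned maximum dropout is still about 10 points short of 80%.

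A third reply is that GI hormones appear among the endpoints to be analysed by ANCOVA, and the plan expects covariates to recover power. With two degrees of freedom spent, the covariates would have to explain about 20% of the variance at 13/13, 23% at 13/12 or 26% at 12/12 to restore 80%. The plan gives no such figure, and the sizing sentence rests on an unadjusted test.

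Finally, the unit does not affect power, because d is unit-free. That is correct; the unit is a reason to check the inputs, not part of the power argument.

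**Conclusion.** The concern holds. As written, the statement that 12 per group give 80% power is not met by the named t-test at 5% on either sidedness: 67.5% two-sided, 78.9% one-sided. On the two-sided reading, 16 evaluable per group are needed, and 36 enrolled keeps 80% only if dropout is about 11% or less. At the planned 30% the chance of missing the planned effect is about 29–31% instead of 20%, so the dismissal of type II error is not supported.

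These figures assume equal variances, an unadjusted test, near-equal losses between arms, and that 3223 and 3125 are right. The last cannot be confirmed from the document: both are printed in mg/dl, a concentration, whereas an AUC is concentration multiplied by time.

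**What to change.** State alpha and sidedness for the primary AUC calculation, and say whether the primary test is the unadjusted t-test or the ANCOVA. For two-sided 5%, replace the sizing sentence with wording such as:

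> Sixteen evaluable participants per group give 80% power (two-sided 5% two-sample t-test, difference 3223, SD 3125). With 36 enrolled, power is about 85% with no dropout, about 80% if 16 of 18 per group complete, about 69–71% at 30% dropout, and 67.5% if 12 per group complete. These figures are for the unadjusted t-test.

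If a one-sided 5% test is intended, declare and justify it, reconcile it with the 95% intervals, and change 12 to 13. If the ANCOVA is to be relied on for power, state and support the assumed proportion of variance explained. In either case, verify 3223 and 3125 against the cited trial, restate them in AUC units, and bring the type II error paragraph into line.

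With enrolment kept at 36 the cost is wording and a less favourable stated power. Holding 80% at 30% dropout under two-sided 5% would instead need 46 participants, 10 more than planned.

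### The 80% power claimed for a 1 kg weight difference does not belong to the weight variable that the plan tests, and on the kg scale it needs an SD of about 1.04 kg with no dropout

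*Combined protocol and SAP*

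**What the plan says.** - **Synopsis, Study design.** The sample size is introduced with "Based on the results of our previous trial comparing weight loss in exenatide therapy vs placebo". It is set at 18 per group, 36 in total, with "80% power, 0.05 alpha to detect a 1 kg difference between treatment and placebo groups". No SD is given, sidedness is not stated and dropout is not mentioned.
- **Secondary Endpoint.** Weight closes a list of measures: "energy expenditure, and body weight in APS-OB phenotype participants intervened with IC-CBAS, compared to placebo". The list does not say whether this means final weight, change in kg or percent change.
- **Statistical Analysis.** The weight effect is tested by ANCOVA "with relative weight loss as the dependent variable, adjusting for gastric emptying" (as T1/2) and gender. Relative weight loss is not defined, no power is stated for it, and baseline weight is not a listed covariate, although weight is measured at Visit 1. This section justifies the same 36 participants differently: 12 per group for a GLP-1 AUC difference, enlarged for up to 30% dropout.
- **Potential Pitfalls.** The risk of a type II error is answered by saying that variation is well characterised, with weight loss at 12 weeks mentioned. No figure for that variation is given.

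**The concern.** A power statement describes one variable, one SD and one number of evaluable participants. Here the statement is in kilograms and the test is in relative loss. The quantities that would link them, a baseline weight and an SD on either scale, are absent.

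Weight loss is part of the hypothesis and of the anticipated results. A reader of the synopsis could take a null weight result as coming from a comparison with 80% power, and nothing in the document supports that. The synopsis also counts all 18 per group, while the statistical section allows for about 12 completers.

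**Working it through.** **1. Can the stated figure be reproduced?** Inputs from the synopsis: difference 1 kg, 18 per group, power 80%, alpha 0.05. The SD is missing, so 18 per group cannot be derived forward. The SD it implies can be back-solved, taking the test as two-sided (an assumption).

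- Normal approximation: SD = 1 / [(1.960 + 0.842) × √(2/18)] = 1 / (2.802 × 0.333) = 1.07 kg.
- Two-sample t-test (noncentral t): the detectable standardised difference is 0.961, so SD = 1 / 0.961 = 1.04 kg.
- If the test were one-sided, the values are 1.21 kg (normal) and 1.18 kg (t).

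**2. Does the claim survive the plan's own dropout allowance?** Statistical Analysis enlarges 12 per group to 12 / (1 − 0.30) = 17.1, rounded up to 18. At SD 1.04 kg, two-sided t-test:

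| Evaluable per group | Power for 1 kg |
|---|---|
| 18 | 80% |
| 12 | 61% |

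**3. How sensitive is it to the SD?** Two-sided t-test, 18 per group, assumed SDs:

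| SD of weight loss (kg) | Power for 1 kg | Difference detectable at 80% power (0.961 × SD) |
|---|---|---|
| 1.04 | 80% | 1.0 kg |
| 1.5 | 49% | 1.4 kg |
| 2 | 31% | 1.9 kg |
| 3 | 16% | 2.9 kg |

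**4. Can 1 kg be read as a relative loss?** Only with a baseline weight, which is not given. At assumed weights of 80, 100, 120 and 140 kg, 1 kg is 1.25%, 1.0%, 0.83% and 0.71%. Power on the percent scale also needs the SD of percent loss. With 18 per group the detectable difference is 0.961 × that SD: 1.9 percentage points if the SD is 2, and 2.9 if it is 3.

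**5. What would Visit 1 weight add to the model?** This was checked by simulation. Assumptions: mean baseline weight 105 kg, within-sex SD 18 kg, all 36 evaluable, a shared lifestyle loss of 4 kg, a 1 kg treatment effect, and losses similar in kg whatever the starting weight. The fitted model has treatment, T1/2 and sex.

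| SD of kg loss | Power, kg loss | Power, percent loss, planned model |
|---|---|---|
| 1.04 | 77% | 58% |
| 1.5 | 49% | 40% |
| 2 | 29% | 25% |
| 3 | 16% | 15% |

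At SD 1.04 kg, adding Visit 1 weight raises percent loss from about 58% to about 73%. At 2 to 3 kg there is little left to recover, because the two scales already differ by only 1 to 4 points.

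If losses are instead proportional to body weight, the covariate gains nothing. In a simpler run with a 3 kg lifestyle loss and without T1/2 and sex, percent loss had 81% power without baseline weight and 79% with it.

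**The case against.** The strongest reply is that Statistical Analysis is the operative section. It sizes the trial on GLP-1 AUC, so the 1 kg sentence is a leftover that governs nothing. Weight is secondary, and the ANCOVA covariates follow the stratification factors. Randomisation keeps the test valid without baseline weight, and percent loss already divides by it. All of this stands. It limits the consequence and makes the covariate an efficiency choice. It does not rescue the power statement: if the sentence is a leftover, it should go.

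Four stronger readings are tempting, and the documents do not support them:

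- **The plan holds three rival definitions of the weight endpoint.** The entry in Secondary Endpoint is an unspecific label, and the synopsis sentence is a sample-size statement. Only Statistical Analysis specifies a weight analysis.
- **A test of exit weight in kg would have almost no power.** No section proposes that test.
- **The kg and percent tests would often disagree.** That depends on the assumed SD and shared lifestyle loss. In the setting of step 5, disagreement is about a quarter of trials (23 to 26%) at SD 1.04 kg but only 5 to 6% at 3 kg.
- **Adding baseline weight makes the scales equivalent.** It brings their power closer. It does not turn kilograms into percent, so one scale with its own SD is still needed.

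**Conclusion.** The point holds as a mismatch between a power statement and the variable tested. The 80% for 1 kg cannot be attached to the ANCOVA of relative weight loss, because no SD or baseline weight is given on which to convert it.

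On its own kg scale the claim requires an SD of about 1.04 kg (two-sided t-test) and complete follow-up. It drops to 61% with 12 completers per group at that SD, and to 49%, 31% and 16% with 18 per group at SDs of 1.5, 2 and 3 kg. These SDs are assumptions, and the documents do not say which is realistic.

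The simulation results rest on further assumptions about baseline weight, sex mix, lifestyle loss and how loss scales with weight. They support the covariate as inexpensive protection, not as the correction of an invalid test. A reader might infer that the trial's main conclusion is at risk, but this point does not touch the primary GLP-1 comparison. The plan should be corrected because weight loss is a prominent claim and the repair is small.

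**What to change.** 1. **Synopsis, Study design.** Delete the 1 kg power statement, or restate it as a percentage-point difference in relative weight loss, with the SD, its source, sidedness and the expected number of completers.
2. **Secondary Endpoint and Statistical Analysis.** Use one definition in both: percent change in body weight from Visit 1 to the day-90 exit visit.
3. **Statistical Analysis.** Add Visit 1 body weight to the weight ANCOVA, beside T1/2 and gender. An adjusted kg difference can be reported as a supporting estimate.

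The cost is wording in three sections and one covariate that is already collected. The covariate uses one degree of freedom, about 1 to 2 points of power if baseline weight explains nothing. No extra participants, visits or procedures are needed. The changes should be made before unblinding, so that the scale is fixed before results are seen.
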